1. PROTOCOL SUMMARY

1.1. Synopsis

Short Title: A study to assess efficacy and safety of PF-06462700 in Japanese participants with aplastic anemia

Rationale

PF-06462700 was evaluated as having high medical needs at the 36th meeting of the Study Group on Unapproved and Off-label Drugs of High Medical Need (held on 17 October 2018), and its development was requested by the Research and Development Division, Health Policy Bureau, Ministry of Health, Labor and Welfare (MHLW) on 12 November 2018 for the request contents described below.

The purpose of the study is to assess the efficacy and safety of PF-06462700 administered intravenously at 40 mg/kg/day for 4 days in Japanese participants with moderate and above aplastic anemia for making an approval application in Japan.

The outline of this study was agreed upon with the Pharmaceutical and Medical Device Agency (PMDA) on 27 September 2019.

Objectives, Estimands, and Endpoints

Objectives	Endpoints	Estimands
Primary:	Primary:	Primary:

• To investigate the efficacy of PF-06462700 administered intravenously at 40 mg/kg/day for 4 days in Japanese participants with moderate and above aplastic anemia	
• Hematologic response at Week 12	
Population: Japanese participants with moderate and above aplastic anemia who are at least 2 years of age
 
Variable: Hematologic response at Week 12
 
Intercurrent events: The efficacy will be evaluated individually for each patient. Therefore, any missing data will not be imputed. All observations after prohibited concomitant medication will be included. Improvement in counts that are dependent upon exogenously administered growth factors or transfusion will not be considered as fulfilling hematologic response criteria in the evaluation.
 
Population-level summary: Due to the limited sample size, summary statistics will not be shown.

Secondary:	Secondary:	Secondary:

• To investigate the efficacy of PF-06462700 administered intravenously at 40 mg/kg/day for 4 days in Japanese participants with moderate and above aplastic anemia	
• Hematologic response at Week 24• Hematological test values at Day 4 and at Weeks 1, 2, 4, 6, 8, 10, 12 and 24 (Absolute neutrophil count, Platelet count, Reticulocyte count). In case of early termination (ET), at ET and follow-up ET.• Survival status• Transfusion independence at Weeks 12 and 24	
Population: Japanese participants with moderate and above aplastic anemia who are at least 2 years of age
 
Variable: Each secondary endpoint
 
Intercurrent events: The efficacy will be evaluated individually for each patient. Therefore, any missing data will not be imputed. All observations after prohibited concomitant medication will be included.
 
Population-level summary: Due to the limited sample size, summary statistics will not be shown.

Safety objective:	Safety endpoints:	Estimands:

• To investigate the safety of PF-	
• Treatment-emergent adverse events	N/A

06462700 administered intravenously at 40 mg/kg/day for 4 days in Japanese participants with moderate and above aplastic anemia	(TEAEs) 
• Serious AEs (SAEs) and AEs leading to discontinuation• Vital signs• Clinical laboratory values	
---	--	--

Overall Design

Study B5411003 will assess the efficacy and safety of PF-06462700 in participants with moderate and above aplastic anemia. This is a multicenter, open-label, single-arm study. The study will have a maximum duration of approximately 28 weeks. This includes an up to 4-week screening period, a 4-day treatment period and a 24-week follow-up period. This study will enroll the minimum of 3 participants. The study will be initially conducted at 3 sites.

Number of Participants

A minimum of 3 participants will be assigned to the investigational product in the study.

Intervention and Duration

The study will have a maximum duration of approximately 28 weeks. This includes an up to 4-week screening period, a 4-day treatment period and a 24-week follow-up period.

Participants will undergo PF-06462700 skin test. Those with a positive skin test will not be administered PF-06462700.

PF-06462700 will be administered at a dose of 40 mg/kg/day for 4 days. PF-06462700 will be infused intravenously over no less than 4 hours. Infusion times may be extended up to 24 hours (including dilution/preparation time) to improve tolerance if necessary.

Data Monitoring Committee: No

[figure not shown]
Statistical Methods

The target sample size was determined based on the study feasibility perspective. No statistical testing and inference will be conducted.

All efficacy analyses will be performed on the full analysis set which includes all participants assigned to the investigational product and who take at least 1 dose of investigational product. The hematological response at Week 12, which is the primary endpoint, will be listed individually for each participant. The sample size is limited; therefore, no summary statistics will be shown. All of the secondary endpoints (described in Section 8.1) will also be listed individually for each patient.

All safety analyses will be performed on the safety population which include all participants assigned to the investigational product and who take at least 1 dose of investigational product. The safety result will be listed individually for each patient.

1.2. Schema

1.3. Schedule of Activities (SoA)

The SoA table provides an overview of the protocol visits and procedures. Refer to the **STUDY ASSESSMENTS AND PROCEDURES** section of the protocol for detailed information on each procedure and assessment required for compliance with the protocol.

The investigator may schedule visits (unplanned visits) in addition to those listed in the SoA table, in order to conduct evaluations or assessments required to protect the well-being of the participant.

	Screening period	Treatment period				Follow-up period								Follow-up of ET case
		Day 1 ^a (baseline)	Day 2	Day 3	Day 4	Day 8 Week 1	Day 15 Week 2	Day 29 Week 4	Day 43 Week 6	Day 57 Week 8	Day 71 Week 10	Day 85 Week 12	Day 169 Week 24 or ET	
Visit Identifier ^a	Screening													Follow up 28 days after ET
Visit Window	Day -28 to -1	N/A	N/A	N/A	N/A	±1 day	±1 day	±3 days	±3 days	±3 days	±3 days	±7 days	±7 days	+7 days
Informed consent/assent	X													
Medical history	X													
Physical examination	X	X			X	X	X	X	X	X	X	X	X	
Vital signs	X	X	X	X	X	X	X	X	X	X	X	X	X	
Weight		X ^c										X	X	
Laboratory														
Hematology	X	X ^b			X	X	X	X	X	X	X	X	X	
Blood chemistry	X	X ^b			X	X	X	X	X	X	X	X	X	
Urinalysis	X	X ^b										X	X	X
HBV, HCV, HIV, HTLV-1	X													
EBV, CMV	X					X ^d	X ^d	X ^d	X ^d	X ^d	X ^d	X ^d	X ^d	
Pregnancy test ^c	X	X ^b					X		X		X	X	X	
Contraception check ^c	X	X ^b					X		X		X	X	X	
12-Lead ECG	X										X	X		
Chest X-ray	X													
Registration		X												
Study treatment														
Skin test		X												

	Screening period	Treatment period				Follow-up period								Follow-up of ET case
		Day 1 ^a (baseline)	Day 2	Day 3	Day 4	Day 8 Week 1	Day 15 Week 2	Day 29 Week 4	Day 43 Week 6	Day 57 Week 8	Day 71 Week 10	Day 85 Week 12	Day 169 Week 24 or ET	
Visit Identifier ^a	Screening													Follow up 28 days after ET
Visit Window	Day -28 to -1	N/A	N/A	N/A	N/A	±1 day	±1 day	±3 days	±3 days	±3 days	±3 days	±7 days	±7 days	+7 days
Investigational treatment administration		X	X	X	X									
Assessments														
Efficacy					X	X	X	X	X	X	X	X	X	
Safety		X	X	X	X	X	X	X	X	X	X	X	X	X
Concomitant treatment(s)	X	X	→	→	→	→	→	→	→	→	→	→	X	X
Serious and nonserious adverse event monitoring	X	→	→	→	→	→	→	→	→	→	→	→	X	X

Abbreviations: Ab = antibody; CMV = cytomegalovirus; EBV = Epstein-Barr virus; ECG = electrocardiogram; ET = Early Termination; HBV = hepatitis B virus, HCV = hepatitis C virus; HIV = human immunodeficiency virus; HTLV-1 = human T-cell leukemia virus type 1; → = ongoing/continuous event, WOCBP = woman of childbearing potential.

- Day relative to start of study treatment (Day 1).
- Hematology, Blood chemistry, Urinalysis, Coagulation, and Pregnancy test on Day 1 can be omitted, if the interval between Screening visit and Day 1 visit is within 7 days.
- For WOCBP only. Monthly urine pregnancy tests and contraception check will be performed by the participant between scheduled study visits starting after the Week 12 visit through the Week 24 or ET visit. Site personnel will contact participants (or their legally authorized representative, if appropriate) between study visits to obtain monthly pregnancy test result and ensure this contact and the result of the pregnancy test are recorded in participant source documentation and CRF.
- EBV DNA or CMV DNA will be performed at Weeks 2, 4, 6, 8, 10, 12 and 24, or ET, or Follow-up of ET for any participant who is EBV Ab or CMV Ab positive at screening.
- If there is body weight data within 3 days before baseline, it can be adopted as a baseline data.

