5.2. Exclusion Criteria

Participants are excluded from the study if any of the following criteria apply:

Medical Conditions:

1. Eligible and willing to have a sibling allogeneic stem cell transplantation.

2. Evidence of a myelodysplastic syndrome (except for refractory cytopenia in children), as well as other primitive marrow disease.
3. History or clinical suspicion of congenital aplastic anemia (Fanconi anemia, Congenital keratosis, etc).
4. History of malignant tumors with active disease within 5 years from study participation.
5. Participants who are clearly infected with hepatitis B virus (HBV), hepatitis C virus (HCV), human immunodeficiency virus (HIV), and human T-cell leukemia virus type 1 (HTLV-1).
6. Pregnant or breast-feeding participants.
7. Participants with severe hepatic, renal or cardiac failure, or any other life-threatening concurrent [aspartate aminotransferase (AST) or alanine aminotransferase (ALT) or total bilirubin values $>5 \times$ upper limit of normal (ULN), and/or creatinine value $>2 \times$ ULN].
8. Participants with hypersensitivity such as shock after skin test of this study drug.
9. Participants with uncontrolled severe infection (pneumonia, sepsis, etc).
10. Participants who received live vaccine or live attenuated vaccine within 6 weeks prior to the first dose of study drug.
11. Other acute or chronic medical or psychiatric condition including recent (within the past year) or active suicidal ideation or behavior or laboratory abnormality that may increase the risk associated with study participation or investigational product administration or may interfere with the interpretation of study results and, in the judgment of the investigator, would make the participant inappropriate for entry into this study.

Prior/Concomitant Therapy:

12. Prior immunosuppressive therapy with lymphocyte-depleting agents/therapies, including both non-B-cell selective and B-cell-depleting agents (e.g., alefacept, alemtuzumab, rituximab). However, participants previously treated with rATG may enroll.
13. Previous history of stem cell transplantation.

Prior/Concurrent Clinical Study Experience:

14. Previous administration with an investigational drug within 30 days (or as determined by the local requirement) or 5 half-lives preceding the first dose of investigational product used in this study (whichever is longer).

Diagnostic Assessments:

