8. STUDY ASSESSMENTS AND PROCEDURES

The investigator (or an appropriate delegate at the investigator site) must obtain a signed and dated ICD before performing any study-specific procedures.

Study procedures and their timing are summarized in the [Schedule of Activities \(SoA\)](#). Protocol waivers or exemptions are not allowed.

Immediate safety concerns should be discussed with the sponsor immediately upon occurrence or awareness to determine if the participant should continue or discontinue study intervention.

Adherence to the study design requirements, including those specified in the SoA, is essential and required for study conduct.

All screening evaluations must be completed and reviewed to confirm that potential participants meet all eligibility criteria. The investigator will maintain a screening log to record details of all participants screened and to confirm eligibility or record reasons for screening failure, as applicable.

Procedures conducted as part of the participant's routine clinical management (e.g., blood count) and obtained before signing of the ICD may be utilized for screening or baseline purposes provided the procedures met the protocol-specified criteria and were performed within the time frame defined in the SoA.

Every effort should be made to ensure that protocol-required tests and procedures are completed as described. However, it is anticipated that from time to time there may be circumstances outside the control of the investigator that may make it unfeasible to perform the test. In these cases, the investigator must take all steps necessary to ensure the safety and well-being of the participant. When a protocol-required test cannot be performed, the investigator will document the reason for the missed test and any corrective and preventive

actions that he or she has taken to ensure that required processes are adhered to as soon as possible. The study team must be informed of these incidents in a timely manner.

The total blood sampling volume for individual participants in this study is approximately 60 mL. The actual collection times of blood sampling may change. Additional blood samples may be taken for safety assessments at times specified by Pfizer, provided the total volume taken during the study does not exceed 550 mL during any period of 60 consecutive days.

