8.2.5. Pregnancy Testing

Pregnancy tests may be urine or serum tests, but must have a sensitivity of at least 25 mIU/mL. Pregnancy tests will be performed in woman of childbearing potential (WOCBP) at the times listed in the [Schedule of Activities \(SoA\)](#). Following a negative pregnancy test result at screening, appropriate contraception must be commenced and a second negative pregnancy test result will be required at the baseline visit prior the participant's receiving the investigational product/study treatment. Pregnancy tests will also be done whenever 1 menstrual cycle is missed during the active treatment period (or when potential pregnancy is otherwise suspected) and at the end of the study. Pregnancy tests may also be repeated if requested by institutional review boards (IRBs)/ethics committees (ECs) or if required by local regulations. If a urine test cannot be confirmed as negative (e.g., an ambiguous result), a serum pregnancy test is required. In such cases, the participant must be excluded if the serum pregnancy result is positive.

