10.2. Appendix 2: Clinical Laboratory Tests

The following safety laboratory tests will be performed at times defined in the SoA section of this protocol. Additional laboratory results may be reported on these samples as a result of the method of analysis or the type of analyzer used by the clinical laboratory; or as derived from calculated values. These additional tests would not require additional collection of blood. Unscheduled clinical laboratory measurements may be obtained at any time during the study to assess any perceived safety concerns.

Table 3. Protocol-Required Safety Laboratory Assessments

Hematology	Chemistry	Urinalysis	Other
Hemoglobin	BUN	Glucose (qual)	At screening only:
Hematocrit	Creatinine	Protein (qual)	
 • FSH^a
RBC count	Glucose (fasting)	Blood (qual)	
 • Pregnancy test (β-hCG)^b
Reticulocyte count	Calcium		
 • Hepatitis B core antibody, surface antibody and surface antigen (HBV DNA if necessary)
MCV	Sodium		
 • Hepatitis C antibody (HCV RNA if antibody is positive)
MCH	Potassium		
 • HIV
MCHC	Chloride		
 • HTLV-1
Platelet count	AST, ALT		
 • EBV antibody (EBV DNA if antibody is positive and conduct at Week 2 and after)
WBC count	Total bilirubin		
 • CMV antibody (CMV DNA if antibody is positive and conduct at Week 2 and after)
Total neutrophils (Abs)	Alkaline phosphatase		
Eosinophils (Abs)	Uric acid		
Monocytes (Abs)	Albumin		
Basophils (Abs)	Total protein		
Lymphocytes (Abs)			

Abbreviations: Abs = absolute; ALT = alanine aminotransferase; AST = aspartate aminotransferase; β -hCG = beta-human chorionic gonadotropin; BUN = blood urea nitrogen; CMV = cytomegalovirus; DNA = deoxyribonucleic acid; EBV = Epstein-Barr virus; FSH = follicle-stimulating hormone; HBV = hepatitis B virus, HCV = hepatitis C virus; HIV = human immunodeficiency virus; HTLV-1 = human T-cell leukemia virus type 1; MCH = mean corpuscular hemoglobin; MCHC = mean corpuscular hemoglobin concentration; MCV = mean corpuscular volume; qual = qualitative; RBC = red blood cell; RNA = ribonucleic acid; WBC = white blood cell.

- For confirmation of postmenopausal status only.

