10.4.2. Female Participant Reproductive Inclusion Criteria

A female participant is eligible to participate if she is not pregnant or breastfeeding, and at least 1 of the following conditions applies:

- Is not a WOCBP (see definitions below in Section 10.4.3).

OR

- Is a WOCBP and using an acceptable contraceptive method as described below during the intervention period (for a minimum of 28 days after the last dose of study intervention). The investigator should evaluate the effectiveness of the contraceptive method in relationship to the first dose of study intervention.

The investigator is responsible for review of medical history, menstrual history, and recent sexual activity to decrease the risk for inclusion of a woman with an early undetected pregnancy.

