3.5.2. Laboratory Data

The following safety laboratory tests will be performed at times defined in the SoA section of this protocol. Additional laboratory results may be reported on these samples as a result of the method of analysis or the type of analyzer used by the clinical laboratory; or as derived from calculated values. These additional tests would not require additional collection of blood. Unscheduled clinical laboratory measurements may be obtained at any time during the study to assess any perceived safety concerns.

As described in SoA section of the protocol, *Hematology, Blood chemistry, Urinalysis, Coagulation, and Pregnancy test on Day 1 (baseline) can be omitted, if the interval between Screening visit and Day 1 visit is within 7 days.* In such cases, the values on screening visit will be used as baseline values.

Table 1. Protocol-Required Safety Laboratory Assessments

Hematology	Chemistry	Urinalysis	Other
Hemoglobin Hematocrit RBC count Reticulocyte count MCV MCH MCHC Platelet count WBC count Total neutrophils (Abs) Eosinophils (Abs) Monocytes (Abs) Basophils (Abs) Lymphocytes (Abs)	BUN Creatinine Glucose (fasting) Calcium Sodium Potassium Chloride AST, ALT Total bilirubin Alkaline phosphatase Uric acid Albumin Total protein	Glucose (qual) Protein (qual) Blood (qual)	At screening only: 
 • FSH^a • Pregnancy test (β-hCG)^b • Hepatitis B core antibody, surface antibody and surface antigen (HBV DNA if necessary) • Hepatitis C antibody (HCV RNA if antibody is positive) • HIV • HTLV-1 • EBV antibody (EBV DNA if antibody is positive and conduct at Week 2 and after) • CMV antibody (CMV DNA if antibody is positive and conduct at Week 2 and after)

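### The Schedule of Activities lets a site skip the Day 1 pregnancy test after recent screening, but Section 8.2.5 requires a second negative test before dosing and states no exception

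*Protocol*

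**What the plan says.** - **Protocol 1.3 (SoA), footnote b.** Several Day 1 laboratory assessments may be skipped after recent screening, and the list ends with the pregnancy test: "Pregnancy test on Day 1 can be omitted, if the interval between Screening visit and Day 1 visit is within 7 days".
- **SAP 3.5.2.** The same allowance, attributed to the SoA: "Pregnancy test on Day 1 (baseline) can be omitted, if the interval between Screening visit and Day 1 visit is within 7 days". Screening values then serve as baseline. This is a copy of the footnote, not independent evidence.
- **Protocol 8.2.5.** Tests in WOCBP follow the SoA timetable. After a negative screening test, contraception has to be started and "a second negative pregnancy test result will be required at the baseline visit prior" to receipt of the product. No exception for recent screening is given.
- **Protocol 1.3, opening paragraph.** The SoA describes itself as an overview and refers to the assessments "section of the protocol for detailed information on each procedure and assessment required for compliance with the protocol".
- **Protocol 5.2, criterion 6.** Excluded: "Pregnant or breast-feeding participants".
- **Protocol 10.4.2.** The investigator reviews medical, menstrual and recent sexual history "to decrease the risk for inclusion of a woman with an early undetected pregnancy".

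**The concern.** The two provisions lead to different conduct for the same woman. If she is screened in the week before Day 1, the footnote allows dosing after one negative test, whereas 8.2.5 asks for two.

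The second test has a purpose. Under 8.2.5 contraception is to be started after the negative screening test, so conception shortly before screening is a foreseeable gap, and the baseline test is the one placed to detect it. If it is skipped, a pregnancy too early to show at screening would not be found by any scheduled test until dosing is over. What is at stake is an eligibility criterion and safety at first dose, together with a compliance question for any site that relies on the footnote. No efficacy endpoint is involved.

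**Working it through.** The plan gives no figure to reproduce. The check compares the texts and counts days.

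**Inputs**
- Screening window Day -28 to Day -1; Day 1 is the start of treatment and is labelled baseline (SoA).
- Doses on Days 1, 2, 3 and 4 (SoA, 6.1.1).
- Omission allowed if screening is within 7 days of Day 1 (footnote b).
- Assumption: there is no Day 0. This agrees with Section 4.1, which puts screening within 28 days before the first dose: from Day -28 to Day 1 is 28 + 1 - 1 = 28 days.

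**Step 1: tests required before dose 1, by screening day**

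| WOCBP screened on | Footnote b | Section 8.2.5 | Conflict |
|---|---|---|---|
| Day -28 to Day -8 | 2 (screening and Day 1) | 2 | No |
| Day -7 to Day -1 | 1 suffices | 2 | Yes, if the omission is used |

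**Step 2: age of the only test when the omission is used**

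With no Day 0, the days from Day -s to Day d are s + d - 1.
- Screening on Day -7: dose 1, 7 + 1 - 1 = 7 days; dose 4, 7 + 4 - 1 = 10 days.
- Screening on Day -1: dose 1, 1 + 1 - 1 = 1 day; dose 4, 1 + 4 - 1 = 4 days.

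The test is therefore 1 to 7 days old at dose 1 and 4 to 10 days old at dose 4.

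**Step 3: next scheduled test**

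As the SoA row reads in the available text, it falls on Day 15. The table's columns may be displaced: the EBV/CMV row starts at Week 1 there, although its footnote starts at Week 2. A shift of one column would put the pregnancy test on Day 8 or Day 29. After a Day -7 screening test the gap is:
- Day 8: 7 + 8 - 1 = 14 days
- Day 15: 7 + 15 - 1 = 21 days
- Day 29: 7 + 29 - 1 = 35 days

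All three days come after Day 4, even at the early edge of the visit windows (Day 7, Day 14 and Day 26). In every reading, 4 of 4 doses precede the next scheduled test.

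**Step 4: number affected**

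The target is 3 participants, of either sex and from 2 years of age, and more may be enrolled (5.1, 9.2). If exactly 3 are enrolled, the number of WOCBP screened within 7 days of Day 1 is between 0 and 3. The documents allow nothing narrower.

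**The case against.** The best defence is that 8.2.5 itself sends the reader to the SoA for test times, so footnote b might be read into it. Section 8 also says that adherence to the requirements in the SoA is essential. This makes the sponsor's intention arguable. It does not remove the conflict: the reference to the SoA governs when tests are done, while the later sentence sets a condition for dosing, a second negative result, without qualification. The SoA also defers to Section 8 for detail. Even a reader who prefers the SoA is left with two texts on which sites could act differently.

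Other safeguards do stand: a screening test at most 7 days old, contraception started after it, exclusion criterion 6, the history review in 10.4.2, and an unscheduled test whenever pregnancy is suspected. The retest adds little after screening on Day -1 and most after Day -7.

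A reader might infer more than the documents support:
- **That no site can comply with both texts.** The footnote only permits omission. Testing every WOCBP on Day 1 meets both.
- **That the sentence "Protocol waivers or exemptions are not allowed" in Section 8 invalidates the footnote.** Section 5 describes waivers as deviations approved in advance. An allowance written into the approved schedule is not plainly one of these.
- **That the contraception check is waived too**, because mark b appears on its Day 1 cell. The footnote does not name that check, and the superscripts are unreliable in the available text (the weight row carries a letter that does not match its note).
- **That the heading "At screening only" above the pregnancy test in protocol Table 3 and SAP Table 1 is further evidence.** The same list includes viral DNA tests to be done from Week 2, so the heading is loose, and Appendix 2 refers to the SoA for timing.
- **That a quarter of participants are exposed**, because 7 of the 28 screening days qualify. That is a share of calendar days, not a probability.

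**Conclusion.** The inconsistency is real and narrow. Footnote b, copied in SAP 3.5.2, permits an omission that 8.2.5 does not provide for. A site using it does not meet 8.2.5 as written and gives all four doses to a WOCBP on one negative test, 1 to 7 days old at dose 1 and at most 10 days old at dose 4.

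The day counts assume no Day 0. The conclusion that the next scheduled test follows the last dose holds for each plausible reading of the damaged table row. The conflict does not depend on footnote lettering, because the footnote's text names the pregnancy test.

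The number affected is small and may be zero. The documents do not say how soon after conception a test would turn positive, so the chance of a missed pregnancy cannot be estimated. No efficacy listing changes. The point should be corrected because it concerns an eligibility safeguard before an exposure that cannot be undone, and because the correction is cheap.

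**What to change.** 1. Delete the pregnancy test from footnote b and from the matching sentence in SAP 3.5.2. The allowance for the other Day 1 laboratory tests can remain.
2. Remove mark b from the Day 1 pregnancy test cell in the SoA.
3. Add to the SoA notes that the Day 1 pregnancy test is done in every WOCBP and must be negative before the first dose.
4. Leave 8.2.5 unchanged.

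Optional tidying: in protocol Table 3 and SAP Table 1, list the pregnancy test as done at the SoA times instead of under the screening-only heading.

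The alternative is to write the 7-day exception into 8.2.5. That removes the contradiction but is weaker, because dosing would still rest on a single test up to 7 days old at dose 1 and 10 days old at dose 4.

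**Cost.** One local urine test, already the protocol's standard method, at the existing Day 1 visit for each WOCBP screened within 7 days of Day 1: at most 3 tests if exactly 3 participants are enrolled. Women screened earlier already have this test. The wording changes need a protocol amendment with IRB/EC approval and a matching SAP edit. No visit is added and the contraception requirements do not change.
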